Multicenter open post-registration study of the safety and effectiveness of the medical device HBIS endoprosthesis of synovial fluid NOLTREX[™] for intraarticular administration in the treatment of gonarthrosis.

Protocol number

IA/PAAG-SI/OA/2020

Studied MD

HBIS endoprosthesis of synovial fluid NOLTREXTM according to TU 9398-00152820385-2015 (hereinafter referred to as NOLTREXTM)

Comparison MD

Not applicable

The duration of the study, the number of research centers and patients

From 29.05.2020 to 31.05.2021, the number of research centers is 4.

Number of patients: a maximum of 72

Purpose of research

Evaluation of the safety and effectiveness of the medical device (MD) NOLTREX[™] for intraarticular administration in the treatment of gonarthrosis of the II–III x–ray stage according to Kellgren-Lawrence.

Tasks of research

1. Evaluation of the safety of MD NOLTREXTM at intraarticular administration in the treatment of gonarthrosis of the II-III radiological stage by Kellgren-Lawrence;

2. Evaluation of the effect of MD NOLTREXTM at intraarticular administration in the treatment of Kellgren-Lawrence stage II–III gonarthrosis on knee function and the need for paracetamol and non-steroidal anti-inflammatory drugs (NSAIDs).

Research method

Study design:

Open-label interventional study in one group with gonarthrosis patients who received a single or double course of injections of MD NOLTREXTM as part of the IA/PAAG-SI/OA/2019 study.

MD NOLTREXTM (synovial fluid endoprosthesis) has been registered for the treatment of osteoarthritis since 2003, and according to annual post-marketing observations it is an effective and safe medical device. A multicenter, double-blind, randomized, comparative, placebo-controlled study of the efficacy and safety of NOLTREXTM for intraarticular administration in the treatment of

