Patients who signed the informed consent form to participate in an open study IA/PAAG-SI/OA/2020 to evaluate the safety and effectiveness of MD NOLTREXTM, in the case when pain in the target knee joint in the study IA/PAAG-SI/OA/2019 remained the same or increased (on a 100-mm visual analogue scale [VAS]) compared to the rating at Visit 1 of the study IA/PAAG-SI/OA/2019 (or if a decrease in pain severity is less than 40— compared to the rating at Visit 1 of the study IA/PAAG-SI/OA/2019), will receive the injection of MD NOLTREXTM in the target knee (Group A). MD will be administered in accordance with the instructions for use of MD NOLTREXTM: 4.0 ml per injection (2.5 + 1.5 ml, or 2.0 + 2.0 ml from two syringes through one needle [one puncture]) at intervals of one week. The course in an open study is a maximum of 2 injections (the first - at Visit 1, the second - at Visit 2). The number of injections is determined by the doctor depending on the stage of gonarthrosis and the clinical response. In order to avoid overfilling the joint with dense slowly resorbable material, at the good clinical result (reducing the pain severity on a 100 mm VAS by Visit

2 by more than 40— compared to the basal level in the open study[1]), the course of injections will be discontinued.

Patients included in the open part of the study, who have the severity of pain in the target knee joint at the time of inclusion in the open part of the study decreased by 40— or more compared to the assessment on Visit 1 of the IA/PAAG-SI/OA/2019 study, or those who cannot be re-injected with MD NOLTREXTM, a re-injection of MD NOLTREXTM will not be performed on Visits 1 and 2 of the open study (Group B).

A repeated course of MD NOLTREXTM injections in an open study is not possible if any of the following criteria are met:

- 1. Documented intolerance of the studied MD NOLTREXTM;
- 2. Active inflammation in the target knee joint (edema, hyperemia, effusion) at the time of inclusion in the study;
- 3. Inflammatory diseases of the skin and soft tissues in the area of the intended introduction of the studied MD into the target joint;
- 4. History of venous thrombosis and thromboembolism;
- 5. Deviations from the norm in the coagulogram (activated partial thromboplastin time [APTT], prothrombin time [PT], prothrombin index, fibrinogen);
- 6. Hemophilia and other hemorrhagic diatheses, as well as taking anticoagulants and disaggregants;

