At Visit 3 additional evaluation will be conducted to assess the feasibility and possibility of reinjections with MD NOLTREXTM among patients of group B. If at Visit 3 of the open study pain remains the same in the target joint of the study IA/PAAG-SI/OA/2019 or increases in intensity (as per 100-mm VAS) in comparison with the assessment at Visit 1 of the study IA/PAAG-SI/OA/2019 (or if a decrease in pain severity is less than 40% when compared to the rating at Visit 1 of the study IA/PAAG-SI/OA/2019), in the absence of the above criteria for non-treatment with the studied MD, at Visit 3 of open study the injection of MD NOLTREXTM into the target knee joint will be performed. MD will be administered in accordance with the instructions for medical use of MD NOLTREXTM: 4.0 ml per injection (2.5 + 1.5 ml, or 2.0 + 2.0 ml from two syringes through one needle [one puncture]) once or twice at intervals of one week. The treatment course in the framework of an open study among patients of Group B is a maximum of 2 injections (the first - at Visit 3, the second - at Visit 4). The number of injections is determined by the doctor depending on the stage of gonarthrosis and the clinical response. In order to avoid overfilling the joint with dense slowly resorbable material, at the good clinical result (reducing the pain severity on a 100 mm VAS by Visit 2 by more than 40— compared to the basal level in the open study[1]), the course of injections will be discontinued. The open nature of the study in one group is determined by the main purpose of the study - to assess the safety of MD NOLTREX[™] with a single or repeated course of use. Placebo safety data at the 6-month point (visit 5) in the IA/PAAG-SI/OA/2019 study will be used as a control. It is assumed that continued monitoring of patients in the placebo group will not lead to the detection of new adverse events (AE), the frequency of which should be compared with the frequency in the active therapy group, and is connected to unethical restriction of patients in the placebo group in the possibility of using potentially effective synovial fluid endoprostheses.

The open study provides follow-up of patients for 6 months (up to 25 weeks from Visit 1).

Thus, the maximum duration of participation in the study for one patient will be a maximum of 172 days.

Patient visits

Visit 0 (Day 0, -24 h -0 h, screening)

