- Assessment of the severity of pain in the target knee joint using 100-mm VAS;
- Evaluation of the effectiveness of treatment by the patient, OEP parameter;
- Evaluation of the effectiveness of treatment by the investigator, OEI parameter;
- Clinical blood test (hemoglobin level, hematocrit, red blood cell count, white blood cell formula, platelet count, ESR);
- Biochemical blood test (glucose, ALT, AST, ALP, GGTP, total bilirubin, creatinine, uric acid, rheumatoid factor);
- Coagulogram (APTT, PT, prothrombin index, fibrinogen)
- General urinalysis (color, transparency, relative density, pH, glucose, protein, ketone bodies, urobilinogen);
- Injection of the studied MD into the cavity of the target joint (only for patients of Group B who are shown to receive the injection according to the criteria specified in the Protocol, and didn't receive the injection at Visit 1);
- Evaluation of the patient's diary;
- Evaluation of the total number of paracetamol tablets taken (one tablet = 500 mg) using patient's diary, PARACETAMOL parameter;
- Evaluation of the patient's diary of the total number of NSAIDs allowed by the Protocol in case of paracetamol inefficiency (NSAIDs allowed by the Protocol in case of paracetamol inefficiency: diclofenac potassium tablets 50 mg, diclofenac sodium tablets 75 mg, naproxen tablets 500 mg, naproxen sodium tablets 550 mg, meloxicam tablets 7.5 mg, celecoxib tablets 200 mg), NSAID parameter;
- Issuing a new patient diary to the patient;
- Registration of AE and SAE;
- Evaluation of exclusion criteria.

Every 2 weeks, between Visit 3 and Visit 4 (weeks 15, 17, 19, 21 and 23), telephone contacts are made with the patient to clarify complaints, AE and the need for taking paracetamol or NSAIDs for the past 2 weeks. If AE is detected, or the need to take paracetamol or NSAIDs more than 4 days a

week in each of the consecutive 2 weeks, the patient is invited to the clinic for an unscheduled Visit or a Visit to prematurely complete participation in the study (depending on the reason for the visit).

Visit 4 (Week 14, Day 91 ± 2, treatment and follow-up) - as indicated

Only patients who received an injection of MD NOLTREXTM into the target knee joint on Visit 3 are eligible for Visit 4.

The following procedures must be performed during the visit:

- Measurement of the body weight;
- Collection of complaints and anamnesis;
- Registration of concomitant therapy;
- Assessment of the main vital signs (BP, HR, RR, body temperature);

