#### **3.1.3.** Analysis of efficacy parameters

Main efficacy parameters of the studied MD:

1. Change in the overall score on the WOMAC scale (WOMAC-T) on Visit 3 (week 13), Visit 5 (week 25) compared to the basal value on Visit 0 (screening) of the open study and compared to the basal value on Visit 1 (week 1) of the IA/PAAG-SI/OA/2019 study;

2. Change in the pain subscale score (WOMAC-A) on Visit 3 (week 13), Visit 5 (week 25) compared to the basal value on Visit 0 (screening) of the open study and compared to the basal value on Visit 1 (week 1) of the IA/PAAG-SI/OA/2019 study;

3. Change in the score for stiffness subscale (WOMAC-B) and functional performance (WOMAC-C) at Visit 3 (week 13), Visit 5 (week 25) compared to the basal value at Visit 0 (screening) of open study and compared to the basal value at Visit 1 (week 1) of the study IA/PAAG-SI/OA/2019;

4. The change in the severity of pain in the target knee on a 100-mm VAS at Visit 2 (week 1), Visit 3 (week 13), Visit 5 (week 25) compared to the basal value at Visit 0 (screening) of open safety study and compared to the basal value at Visit 1 (week 1) study IA/PAAG-SI/OA/2019;

5. Evaluation of the effectiveness of treatment by the patient, parameter OEP (on a scale from 1-clear deterioration to 6-significant improvement) on Visits 3 and 5 (parameters OEP-w13 and OEP-w25, respectively);

6. Evaluation of the effectiveness of treatment by the investigator, parameter OEI (on a scale from 1-clear deterioration to 6-significant improvement) on Visits 3 and 5 (parameters OEI-w13, OEI-w25, respectively);

7. Assessment of the total number of paracetamol tablets taken (one tablet = 500 mg) starting from day 1 on Visits 3 and 5 (PARACETAMOL -w13 and PARACETAMOL-w25, respectively);

8. Assessment of the total number of NSAID tablets taken starting from day 1 on Visits 3 and 5 (NSAID-w13 and NSAID-w25, respectively);

9. The parameter JSN of the target knee joint at Visit 5 of the open study compared to the basal value on Visit 0 of the IA/PAAG-SI/OA/2019 study retrospectively.

All performance parameters will be analyzed both among all patients included in open study no. IA/PAAG-SI/OA/2020 (using descriptive statistics) and in subgroups of patients:

- those who received only one course of injections in the placebo-controlled study IA/PAAG-SI/OA/2019;
- those who received two courses of therapy both in the placebo-controlled and at Visit 1 (and as per the indications at Visit 2) of the open study;

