- those who received two courses of therapy both in the placebo-controlled and at Visit 3
  (and as per the indications at Visit 4) of the open study.

For comparison between these subgroups, variance analysis will be used (for quantitative parameters other than those based on WOMAC), covariance analysis (for quantitative parameters based on WOMAC, in this case the initial value of WOMAC in the double-blind phase of the study will be used as a covariate, and the results will be presented as the average, calculated by the least squares method), or the "Chi-square" criterion (for qualitative parameters), followed by the application of multiple comparison criteria (if necessary).

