## **3.6.** Procedures to count the missing, non-analyzable, and questionable data

During the monitoring visits to the clinical center, the monitoring specialists authorized by the sponsor will conduct an analysis of patient's eCRF to identify any lack of necessary data. In the absence of data in the eCRF and the availability of relevant information in the primary documentation, the questions to the investigators and instructions for eliminating the inconsistencies will be formulated.

The statistician, authorized by the sponsor, and the principal investigator, when checking the database of research results, will analyze for the presence of dubious, missing and non-analyzable data, and will also formulate questions for investigators.

Researchers, if possible, will eliminate the identified errors in eCRF and inform the main researcher and authorized representatives of the sponsor about this. If the detected errors in the data cannot be eliminated after the completion of patient participation in the study, the statistical analysis of the data will be used to analyze the sensitivity of the resulting parameters to the doubtful data found. Information about the missing, doubtful and non-analyzable data will be presented in the final clinical trial report.

For all parameters of efficacy, safety and tolerability, data recovery is not provided due to the fact that the distribution of patients into subgroups for analysis is based on the actual need for treatment, and is not based on any procedures for distribution into groups, so the missing values cannot be considered as missing accidentally or completely accidentally.

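### SAP 3.1.3 tests VAS and WOMAC change between subgroups formed on the same VAS readings, so the tests cannot show an effect of re-injection

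*SAP*

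**What the plan says.** SAP 3.1.3 sets three subgroups by treatment actually received: the 2019 course only, a second course starting at open-study Visit 1, and a second course starting at Visit 3. The whole group is summarised descriptively, but the subgroups are tested against each other. For VAS change, "variance analysis will be used (for quantitative parameters other than those based on WOMAC", with no covariate named. WOMAC change goes into an ANCOVA in which "the initial value of WOMAC in the double-blind phase of the study will be used as a covariate". Multiple-comparison procedures follow if needed. Change is taken from two baselines, "compared to the basal value on Visit 0 (screening) of the open study and compared to the basal value on Visit 1" of the 2019 study. SAP 3.4 applies a two-sided 5% level to all efficacy parameters.

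The Study design part of the protocol decides who is in which subgroup. Group A is re-injected at Visit 1 if pain is unchanged or higher than at 2019 Visit 1, or if the "decrease in pain severity is less than 40" percent (the sign is garbled there but legible in the Visit 3 rule). Group B has a fall of 40% or more, or is barred from re-injection whatever the pain. Group B is reassessed at Visit 3, and the same test applies: pain no lower, or the "decrease in pain severity is less than 40% when compared to the rating at Visit 1 of the study". The Visit 3 procedures list the injection "only for patients of Group B who are shown to receive the injection according to the criteria specified in the Protocol".

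SAP 3.6 recognises that "the distribution of patients into subgroups for analysis is based on the actual need for treatment", but uses this only to rule out imputation.

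**The concern.** Task 2 of the protocol is to evaluate the device's effect "on knee function and the need for paracetamol and non-steroidal anti-inflammatory drugs (NSAIDs". The subgroup tests in SAP 3.1.3 are the only planned efficacy comparisons of one course with two, so their p-values are likely to be read as evidence for or against a repeat course.

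The subgroups differ in pain because they were sorted on pain. A patient selected for a high reading tends to read lower next time, and one selected for a low reading tends to read higher. When the selecting reading is also the baseline, this regression to the mean enters the change score directly. The two planned baselines can then give opposite significant answers for the same patients with no treatment effect at all.

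**Working it through.** **1. Roles of each VAS reading**

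| Reading | Role in forming subgroups | Role in the analysis |
|---|---|---|
| 2019 Visit 1 | Reference for both 40% rules | Second baseline |
| Visit 0 (taken from 2019 Visit 5) | Separates Group A from Group B | First baseline |
| Visit 3 | Splits Group B | Tested outcome |
| Visit 5 | None | Tested outcome |

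The protocol lists no VAS at open-study Visit 1, so the Visit 0 reading both selects Group A and serves as its baseline.

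**2. What follows from the rules alone**

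A fall of less than 40% means a current VAS above 0.6 × the 2019 value. For a 2019 value of 60 mm the cut is 0.6 × 60 = 36 mm. At Visit 3, a Group B patient who is not barred is injected if above 36 mm and stays one-course if at or below it. The Visit 3 difference between these patients exists before the injection and cannot be caused by it.

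**3. Null simulation**

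The plan has no power figure to reproduce; 72 is the size of the 2019 device arm. The documents give no SDs or correlations, so these inputs are assumed: 2019 VAS mean 65 (SD 13), SD 18 at later visits, mean fall to Visit 0 of 45%, correlation 0.7 between open-study visits, nobody barred, no drift and zero re-injection effect. Mean VAS (mm):

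| Subgroup | Share | 2019 | Visit 0 | Visit 3 | Visit 5 |
|---|---|---|---|---|---|
| One course | 0.44 | 65.4 | 23.5 | 23.5 | 26.2 |
| Re-injected at Visit 1 | 0.42 | 64.8 | 50.9 | 45.5 | 45.5 |
| Re-injected at Visit 3 | 0.14 | 65.0 | 30.2 | 47.1 | 38.0 |

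The whole-group mean does not move: at Visit 0 it is 0.44 × 23.5 + 0.42 × 50.9 + 0.14 × 30.2 = 36.0, and at Visit 5 it is 0.44 × 26.2 + 0.42 × 45.5 + 0.14 × 38.0 = 36.0. The subgroups move only because of how they were selected.

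Difference in change = (subgroup outcome − subgroup baseline) − (one-course outcome − one-course baseline). Positive means the re-injected look worse.

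- Re-injected at Visit 1, Visit 5, from Visit 0: (45.5 − 50.9) − (26.2 − 23.5) = −8.1 mm (−8.2 unrounded).
- The same patients and visit, from 2019: (45.5 − 64.8) − (26.2 − 65.4) = +19.9 mm.
- Re-injected at Visit 3, Visit 3: from Visit 0, (47.1 − 30.2) − (23.5 − 23.5) = +16.9 mm; from 2019, (47.1 − 65.0) − (23.5 − 65.4) = +24.0 mm.
- Re-injected at Visit 3, Visit 5: from Visit 0, (38.0 − 30.2) − (26.2 − 23.5) = +5.1 mm; from 2019, (38.0 − 65.0) − (26.2 − 65.4) = +12.2 mm.

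With 20% barred and half of them eligible again by Visit 3, the four Visit 5 differences become −7.3, +17.7, +3.7 and +12.0 mm.

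**4. False rejection at n = 72**

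Overall test at Visit 5, for open-visit correlation 0.5, 0.7 and 0.85:

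| Test | From Visit 0 | From 2019 |
|---|---|---|
| VAS ANOVA | 97%, 80%, 55% | 79%, 100%, 100% |
| WOMAC ANCOVA (VAS-WOMAC correlation 0.7) | 66%, 44%, 26% | 48%, 89%, 99% |

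A wider set of null settings (15% barred; linear and responder models) gave these Bonferroni-adjusted pairwise rates for VAS change from Visit 0 against one course:

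- Re-injected at Visit 1, falsely better: 5-70% at Visit 3 and 7-84% at Visit 5.
- Re-injected at Visit 3, falsely worse: 48-97% at Visit 3 but only 5-21% at Visit 5.

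In a further adjusted run, opposite significant answers from the two baselines for Visit 1 re-injection at Visit 5 came in 9-46% of trials. In one setting this was 39% at n = 72 and 12% at n = 40.

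**5. How stable the directions are**

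Two re-injected subgroups, two baselines and two visits give eight VAS differences. All eight had the expected sign in 541 of 588 scenarios, and in 84 of 84 with nobody barred. The other 588 − 541 = 47 had 20-40% barred and a mean fall of only 30%. This count leaves out a pattern where the Visit 0-Visit 5 correlation decays to 0.3 × 0.3 = 0.09; including it, 581 of 672 agree.

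**The case against.** Safety is the main purpose, no single primary efficacy endpoint is named, and the documents say openly that the subgroups follow need for treatment. No passage says that these p-values will support a repeat course, and SAP 3.1 refers to a fuller plan. All of this limits the severity. It does not make the tests interpretable, and multiple-comparison procedures control multiplicity, not selection.

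A reader might also infer stronger claims that the documents do not support:

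- *The Visit 3 groups separate completely on the tested endpoint.* The rule separates patients who are not barred on the ratio to 2019, but the SAP tests change in mm. A fall from 90 to 55 mm is 35/90 = 38.9% (injected, −35 mm). A fall from 40 to 20 mm is 50% (not injected, −20 mm). The mm changes can overlap; the bias remains.
- *The directions always hold.* Group B includes barred patients whatever their pain, the bars are broad, and the barred share is not stated. With many barred and a small mean fall, single differences can vanish or reverse.
- *Visit 3 re-injection looks clearly worse throughout.* From Visit 0 at Visit 5 the difference was about 4-5 mm in the main scenarios with nobody barred. Adjusted significance came in 6-10% of trials and the opposite sign in 13-21%.
- *The simulated rates are what this trial would show.* They use n = 72, which is a maximum, and rates fall with fewer patients.
- *Every subgroup efficacy test fails in the same way.* The two-baseline conflict concerns VAS and WOMAC change only. OEP, OEI and JSN were not simulated, and tablet counts only under an assumed correlation with pain.

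**Conclusion.** The between-subgroup tests of VAS and WOMAC change cannot show a re-injection effect and should not stand as inferential comparisons. That follows from the protocol's selection rules and the SAP's choice of baselines and outcomes, without any simulation.

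The direction of the bias holds under most plausible assumptions, not all. Visit 1 re-injection looks better from Visit 0 and worse from 2019, and Visit 3 re-injection looks worse at Visit 3 from both baselines. Its Visit 5 difference from Visit 0 is weak. The sizes are illustrative, because SDs, correlations and the barred share are not in the documents. The whole-group descriptive efficacy summary and the study's safety purpose are not affected by this point. It is worth correcting, but it is not a flaw in the study's main aim.

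**What to change.** In SAP 3.1.3, or in the fuller plan that SAP 3.1 mentions, replace the subgroup tests of VAS and WOMAC change with wording such as:

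> VAS and WOMAC parameters will be summarised by subgroup with 95% CI, including observed values at each visit where they were assessed. No between-subgroup tests will be done. The subgroups are defined by pain at Visit 0 and Visit 3 relative to Visit 1 of IA/PAAG-SI/OA/2019, together with eligibility for re-injection. Differences between them, and change from Visit 0 within them, do not estimate the effect of re-injection.

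The within-subgroup clause is needed because Group A alone changed by −1.3 to −13.3 mm from Visit 0 under the null settings.

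Present OEP, OEI, tablet counts and JSN by subgroup with the same statement. Label any comparison exploratory and non-causal, because the subgroups follow need for treatment. Limit SAP 3.4 to the tests that remain.

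Do not substitute an ANCOVA on the selecting VAS values. Apart from barred patients, those values determine assignment, so the result rests on model extrapolation. In null runs of Group A against Group B it rejected in 4-7% of trials under a linear model but 20-70% under a responder model, with a spurious +8.5 to +17.8 mm.

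The cost is the loss of formal between-subgroup p-values for VAS and WOMAC. Only wording changes: no new data or procedures, and no clinical rule is touched. Little is lost, since no sample size was calculated for these comparisons.

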- Evaluation of the effectiveness of treatment by the patient, parameter (on a scale from 1-clear deterioration to 6-significant improvement) on Visits 3 and 5 (parameters OEP-w₁₃ and OEPw₂₅, respectively);
- Evaluation of the effectiveness of treatment by the investigator, parameter (on a scale from 1clear deterioration to 6-significant improvement) on Visits 3 and 5 (parameters OEI-w₁₃, OEIw₂₅, respectively);
- Assessment of the total number of paracetamol tablets taken (one tablet = 500 mg) starting from day 1 at Visit 3 and 5 (parameters PARACETAMOL-w₁₃ and PARACETAMOL-w₂₅, respectively);
- Assessment of the total number of NSAID tablets taken starting from day 1 at Visits 3 and 5 (parameters NSAID-w₁₃ and NSAID-w₂₅, respectively);
- 9. The parameter JSN of the target knee joint at Visit 5 of the open study compared to the basal value on Visit 0 of the IA/PAAG-SI/OA/2019 study retrospectively.

All performance parameters will be analyzed among all patients included in open study no. IA/PAAG-SI/OA/2020, as well as in subgroups of patients:

- who received only one course of injections in the placebo-controlled study IA/PAAG-SI/OA/2019;
- those who received two courses of therapy both in the placebo-controlled and at Visit 1 (and as per the indications at Visit 2) of the open study;
- those who received two courses of therapy both in the placebo-controlled and at Visit 3 (and as per the indications at Visit 4) of the open study.

Inclusion criteria

The study will include patients who meet all these criteria:

- 1. Men and women over 50 years of age;
- 2. Signed informed consent form for the study participants;

3. Verified gonarthrosis according to ACR criteria (knee pain in combination with one of the following signs: age over 50 years, crepitation in the joint or morning stiffness in the joint lasting less than 30 minutes in combination with radiological signs of gonarthrosis);

4. II-III radiological stage of gonarthrosis according to the Kellgren-Lawrence classification with a predominant lesion of the medial tibiofemoral section of the knee joint;

5. Completion of participation in the IA/PAAG-SI/OA/2019 clinical trial in the group with NOLTREX[™] medical device through Visit 5 (25 weeks).

Non-inclusion criteria

Patients cannot be included in the study if they have at least one of the following criteria for noninclusion:

- 1. Pregnancy or breast-feeding;
- 2. History of injury or surgery on the target knee joint;

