#### 3.1.1. Demographic data, baseline data, and follow-up data.

As part of this open continuation study, an initial (on Visit 0) assessment of parameters similar to those for the double – blind IA/PAAG-SI/OA/2019 study will be performed, and data from the group originally included in the IA/PAAG-SI/OA/2019 study that received the medical device under study and the group that was included in the current open study will be compared. This comparison will be performed using descriptive statistics.

In addition, the initial characteristics will be compared depending on the actual distribution into the following subgroups:

- who received only one course of injections in the placebo-controlled study IA/PAAG-SI/OA/2019;
- those who received two courses of therapy both in the placebo-controlled and at Visit 1 (and as per the indications at Visit 2) of the open study;
- those who received two courses of therapy both in the placebo-controlled and at Visit 3 (and as per the indications at Visit 4) of the open study.

For comparison between these subgroups, variance analysis (for quantitative parameters) or the "Chisquare" criterion (for qualitative parameters) will be applied, followed by the application of multiple comparison criteria (if necessary).

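### The between-subgroup efficacy models in SAP 3.1.3 omit Kellgren-Lawrence stage, a baseline factor that could confound them indirectly; add it together with the VAS values that drive allocation

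*SAP*

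**What the plan says.** **Models.** For the comparison of subgroups, SAP 3.1.3 says "variance analysis will be used (for quantitative parameters other than those based on WOMAC"; this covers VAS, tablet totals and JSN, and no covariate is named. WOMAC quantities get an analysis of covariance whose single covariate is the initial WOMAC of the double-blind phase. Qualitative parameters get a chi-square test. SAP 3.4 sets a two-sided 5% level.

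**Subgroups.** They are defined by whether and when a second course was given: none, from Visit 1, or from Visit 3. SAP 3.6 acknowledges that membership follows treatment need rather than an allocation procedure.

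**Stage.** Inclusion criterion 4 of the Protocol requires "II-III radiological stage of gonarthrosis according to the Kellgren-Lawrence classification". Under Study design, the Protocol says "The number of injections is determined by the doctor depending on the stage of gonarthrosis and the clinical response", and also "The course in an open study is a maximum of 2 injections".

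**Entry to a second course (Protocol, Study design).** Group A are patients whose target-knee pain "remained the same or increased (on a 100-mm visual analogue scale [VAS]) compared to the rating at Visit 1" of the 2019 study, or fell by less than 40%. Group B are patients with a fall of 40% or more, or "those who cannot be re-injected with MD NOLTREXTM". At Visit 3 the VAS rule is applied again to Group B and, "in the absence of the above criteria for non-treatment with the studied MD, at Visit 3 of open study the injection" is given.

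**Baseline comparison.** SAP 3.1.1 says "In addition, the initial characteristics will be compared depending on the actual distribution into the following subgroups". It does not name stage, and SAP 3.1.3 uses nothing from it.

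**The concern.** The subgroups select themselves through the course of the disease, so a baseline factor related both to first-course response and to outcome can appear as a subgroup difference. Stage is a natural candidate. JSN is the clearest case: it is radiographic, as stage is, so the relevance of stage to JSN does not depend on the pain rule, and JSN is compared with no adjustment at all.

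If stage III knees respond less well to the first course, they will be over-represented among patients who receive a second. Any worse outcome that goes with stage would then be read as a feature of the repeat course, possibly with a p-value below 0.05. If stage is balanced there is no bias, and the models only carry avoidable residual variance.

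**Working it through.** The plan has no calculation to reproduce. The figure of 72 is the number randomised to the device in the 2019 study, and no formal sample size was computed. The documents give no stage shares, stage effects or SDs, so every input below other than 72, the 40% rule and the 5% level is an assumption.

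**1. Where stage enters.**

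| Decision | What the Protocol bases it on | Stage named? |
|---|---|---|
| One or two injections within a course (Study design) | Stage and clinical response | Yes |
| Second injection (Visit 2 and Visit 4 procedures) | 40% VAS rule | No |
| Second course from Visit 1 | 40% VAS rule and re-injection criteria | No |
| Second course from Visit 3 | The same rule and criteria | No |

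The subgroups correspond to the last two rows. Stage can reach them only through its association with pain response.

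**2. Size of the bias from stage.** Bias in SD = (difference in stage III share) x (stage effect in SD).
- 20 points and 0.3 SD: 0.20 x 0.3 = 0.06 SD.
- 40 points and 0.8 SD: 0.40 x 0.8 = 0.32 SD.
- Equal shares: 0.

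The two factors are not independent if stage acts through response. With half the patients at stage III and a rule that splits patients in half, the stage III share among non-responders is Φ(d/2). For d = 0.8 that is Φ(0.4) = 0.655, so about 66% v 34%, and the bias is 0.31 x 0.8 = 0.25 SD. For d = 0.3 it is Φ(0.15) = 0.56, so 56% v 44%, and the bias is 0.12 x 0.3 = 0.04 SD. The top of the range therefore needs more imbalance than this mechanism alone would produce.

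**3. Effect on the test.** For two groups of 36, the rejection rate is Φ(δ/√(2/36) − 1.96) + Φ(−δ/√(2/36) − 1.96). A bias of 0.1 SD gives 7.1%, 0.2 SD gives 13.6% and 0.32 SD gives 27.4%.

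For the three-group F-test, the simulation used a 30/27/15 split, stage III shares of 40/60/50% or 30/70/50%, stage effects of 0.3 to 0.8 SD and 5,000 runs per setting. The unadjusted test rejected in 5.5% to 15.6% of runs (4.7% to 14.8% in a repeat). With stage as a factor it rejected in 4.7% to 5.3% (4.4% to 5.5% in the repeat). The return to 5% is built in, because stage was the only difference between the simulated subgroups.

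**4. Precision if stage is balanced.** Share of residual variance removed at 50% stage III = (d²/4)/(1 + d²/4). For d = 0.5: 0.0625/1.0625 = 5.9%. For d = 0.8: 0.16/1.16 = 13.8%.

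**5. Is stage enough?** This simulation has no course effect. It uses 72 patients, half at stage III, SD 20 mm and a residual correlation of 0.6 between the two later VAS readings. Two groups are formed by the 40% rule alone, with 1,500 runs per row. The outcome is VAS change from 2019 Visit 1.

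| Stage effect (SD) | Unadjusted difference, mm (% significant) | Plus stage | Plus stage and both VAS values |
|---|---|---|---|
| 0 | 18.3 (98.8) | 18.3 (98.7) | −0.6 (5.0) |
| 0.2 | 18.8 (99.3) | 18.6 (99.2) | −0.5 (5.0) |
| 0.5 | 20.1 (99.8) | 18.9 (99.3) | 0.2 (4.6) |
| 0.8 | 21.9 (100) | 18.9 (98.5) | −0.1 (4.7) |

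At a stage effect of 0.5 SD, adding stage moves the difference from 10.8 to 9.3 mm when the correlation is 0.3, and from 26.1 to 25.2 mm when it is 0.8. In the table, stage accounts for at most 21.9 − 18.9 = 3.0 mm. Selection on VAS response accounts for the rest. JSN was not simulated.

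**The case against.** A reader might infer from the Study design sentence on stage that stage decides who has one course and who has two. The documents do not support that. The sentence concerns one or two injections within a course, and the subgroups pool patients with one and two injections. Entry to a second course depends on VAS response and on a list of criteria that does not include stage. This part of the objection stands in full, and it limits the point to indirect confounding. Separately, Study design lets stage influence the second injection while the Visit 2 and Visit 4 procedures give a VAS rule only; those texts must be reconciled.

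The second objection is that the larger bias lies elsewhere, and that least-squares means adjusted for stage alone could make a still-confounded comparison look corrected. Step 5 bears this out. It is a reason to widen the adjustment, not to leave stage out.

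Third, safety is the main purpose, no efficacy hypothesis is set, SAP 3.1 calls its own description brief, and the SAP 3.1.1 comparison could reveal a stage imbalance. This lowers the weight of the point. It does not remove it: the comparisons are still tested at 5%, and detecting an imbalance does not adjust for it.

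Fourth, the sizes are assumed. They are, and at the mild end the inflation is negligible.

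**Conclusion.** The point holds as a modest, inexpensive improvement. No between-subgroup model contains stage, allocation is not randomised, and stage has to be known for every patient. Confounding by stage is possible but indirect. Its size is unknown: 0.06 to 0.32 SD for assumed differences of 20 to 40 points in stage III share and stage effects of 0.3 to 0.8 SD, and zero with equal shares. In the balanced case stage removes about 6% to 14% of residual variance for effects of 0.5 to 0.8 SD at 50% stage III.

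A reader might also infer that adding stage would make the subgroup differences interpretable as effects of a repeat course. It would not. Under the assumptions of step 5, about 18 to 19 mm of spurious VAS difference remains after stage is added. The near-zero result with both VAS values is also favourable to the method, since the simulated relation is close to linear and only two groups are formed.

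**What to change.** In SAP 3.1.3:
- Add stage (II/III) as a fixed factor in the between-subgroup ANOVA and ANCOVA models for quantitative parameters. Take it as recorded for inclusion criterion 4 or from the 2019 study film, since the only radiograph listed in the open study is at Visit 5.
- In the same models, add the VAS values that drive allocation: 2019 Visit 1 VAS and open-study Visit 0 VAS.
- Keep the unadjusted results as secondary.
- Label the subgroup comparisons exploratory, and state that they do not estimate the effect of a repeat course.
- Do not stratify the qualitative tests by stage. Six-level OEP or OEI by three subgroups by two stages gives 6 x 3 x 2 = 36 cells, an average of 72/36 = 2 patients per cell at most.

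In SAP 3.1.1, tabulate stage by subgroup.

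**Cost.** No new data and three degrees of freedom per model. With 72 patients, residual degrees of freedom fall from 69 to 66 in the ANOVA and from 68 to 65 in the ANCOVA. Adjustment remains limited: the 40% rule nearly determines membership, so the adjusted contrast leans on the assumed form of the VAS relation, and the Visit 3 subgroup is defined after baseline.
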